We plan to comply with the sIRB plan by obtaining consent from UNC's Institutional Review Board. University of Cincinnati and Cincinnati Children's Hospital and Medical Center will rely on UNC's approval with sites signing an authorization/reliance agreement that will clarify the role and responsibilities of the sIRB and the relying sites. Communication between the OH site and the UNC IRB will be facilitated by the UNC study project manager, [name]. UNC Department of Nutrition and the UNC IRB will maintain the records for the authorization/reliance agreements along with documentation of the associated communication plan.

14. Data Safety & Monitoring:

Data Safety and Monitoring Plan

To ensure timely completion of the study, MPIs [name] and [name], study endocrinologists ([name] and [name]) and program manager ([name]), will constitute the study Executive Committee that will meet weekly during the first six months and bi-weekly thereafter to oversee progress, participant well-being, data quality and completion, and problem-solve as needed. A 3-member DSMB will be convened to meet three times over the course of the study via video conference call. These meetings will be held prior to the start of the study, mid-way through the study, and at the end of the study. DSMB members represent expertise in endocrinology, nutrition, and study design and statistical analysis. Prior to the start of the study, the DSMB will review and approve the final study protocol and any significant changes to the protocol over the course of the study especially as related to participant burden or safety. Midway through the study, the DSMB will meet to monitor and advise on study participant accrual and retention, progress and completeness for all standardized measurement visits and attendance at intervention sessions. Data quality will be reviewed and staff training and certification will be monitored. Adverse events will be monitored. A summary of the DSMB report will be sent to both the local site IRBs and NIDDK as part of the annual progress reports.

Members of the DSMB have been identified by area of scientific expertise (all with relevant expertise applied to T1D), are non-conflicted, and have agreed to serve:

- Pediatric Endocrinology: [name], PhD, MPH Associate Professor of Pediatrics and Epidemiology, Director, Diabetes Program, UPMC Children's Hospital of Pittsburgh
- Nutrition: [name], Associate Professor, Department of Rehabilitation, Exercise and Nutrition Sciences, University of Cincinnati
- Study Design and Statistical Analysis: [name], Gillings School of Global Public Health, University of North Carolina, Chapel Hill

Data Monitoring

Questionnaires will be administered to participants. Data will also be obtained via CGM, HbA1c point of care measurement, and dietary recalls. All aspects of data collection and data storage will be carefully monitored to ensure rapid detection of errors, inconsistencies or other problems. The data collectors will follow a strict written protocol that describes study measures for protecting data privacy. They will explain to each participant that s/he has the right to refuse to participate or to refuse to answer any individual question that s/he finds objectionable, and emphasize the importance of telling the truth. All institutions associated with this application are experienced in training data collection fieldwork personnel how to handle, store, and process sensitive and confidential data. Certain routine administrative, personnel, physical security, information management, and computer system or network security practices are always in

place. These practices include building and audio-tape vault security, non-disclosure pledges, and account/keyword security on computer networks. In addition, we take multiple project-specific steps to protect subjects from the risk of a breach in confidentiality. All data will be collected using study identification numbers. Thus, no questionnaire will contain identifying information, and the list that links identification numbers to names will be kept in a password-protected file that is accessible only to authorized staff at the respective clinical sites. Only aggregate data that cannot be used to identify individuals will be included in any reports released to other agencies or for publication.

Adverse Events

The intervention will involve individuals with T1D who are 12-17 years of age. It is unlikely that participation in our studies will cause youth to experience an “adverse event.” However, trained staff will be conducting the intervention sessions to address any potential issues. Any youth experiencing hypo/hyperglycemia or an otherwise potentially expected symptom related to diabetes will be encouraged to consult their diabetes care provider or to go to the emergency room immediately as needed.

For purposes of monitoring and reporting adverse events, the following NIH definitions will be used:

Adverse Event (AE): any unanticipated, untoward medical occurrence that may present itself during treatment or administration of an intervention, and which may or may not have a causal relationship with the treatment. Adverse events could arise from the study (e.g., breach of confidentiality) or could arise due to the population under study.

Serious Adverse Event (SAE): Any medical occurrence that results in death; is life-threatening; requires inpatient hospitalization or prolongation of existing hospitalizations; creates persistent or significant disability/incapacity, or a congenital anomaly/birth defect.

It is highly unlikely that participation in the dietary intervention will cause an AE or SAE. Should an AE occur, however, the research dietitian and study coordinator will immediately report any AE's connected to the implementation of the intervention to the study investigators, who will keep a log of AE's and SAE's. The log will also be used to provide information about AE's in annual progress reports to participating IRBs and NIDDK.

Our team will file a written report to the site IRBs in accordance with local IRB requirements, and to NIDDK. Outcomes for AE's will be monitored by the DSMB and outcome information will be entered into a log for inclusion in reports to participating IRBs and NIDDK as required. Anticipated events relative to the population under study or relative to the study (e.g., low or high blood glucose) will be noted as potential risks on the informed consent form. The DSMB will also monitor the occurrence of these events. Should any other problems or concerns arise with the data collection or intervention program, the PI or local clinical PI will be available to address these. In addition, resource

and referral listings for community services will also be provided on a routine basis as needed. Drs. [name], [name], [name] and [name] will also work extensively with the staff at each of the clinics to ensure that if adolescents need to be referred that these situations are managed in a manner consistent with clinic preferences/ policies.

The following grading scale will be used to adjudicate AE/SAEs.

Study Relatedness:	Action Taken:	Status:
1=Definitely Unrelated	0 = None	1 = Resolved
2=Possibly Related	1 = Counteractive Medication	2 = Recovered with minor sequelae
3=Probably Related	2 = Medical/surgical intervention	3 = Recovered with major sequelae
4=Definitely Related	3 = Hospitalization	4 = Condition still present and under treatment
5=Diabetes Related; Definitely Unrelated	4 = Other (specify under comments)	5 = Condition continues to worsen
		6 = Patient died

All AEs will be reviewed by the study Data and Safety Monitoring Board to determine if an AE is related to the research project. Our team will file a written report to the site IRBs in accordance with local IRB requirements. Outcomes for AE's will be monitored by the DSMB and outcome information will be entered into a log for inclusion in reports to participating IRBs and NIDDK as required.

Anticipated events relevant to the population under study (e.g., low or high blood glucose) will be noted as potential risks on the informed consent form. The DSMB will also monitor the occurrence of these events. The study PIs will also work with the staff at each of the clinics to ensure that if participants need to be referred, these situations are managed in a manner consistent with clinic preferences/policies.

Should any other problems or concerns arise with the data collection or intervention program, the PI or local clinical PI will be available to address these.

15. Privacy & Confidentiality

In-person recruitment will occur in the diabetes clinics by study personnel. Study visits will occur in private settings or on secure videoconference platforms. Unencrypted messaging will only occur between study personnel and parents reminding them of study sessions, encouraging them to complete questionnaires or other study activities, and only if they consent. Encrypted e-mails and text messages will be sent to minors to encourage and remind them.

To minimize the risk of loss of confidentiality, all information related to study subjects will be confidential and kept in a locked cabinet or in password-protected computer files, in compliance with NIH and HIPAA requirements as detailed in NIH Notice OD-020 issued December 30, 2004.

Each participant will be assigned a unique study identification (ID) number. Participants will be identified on all study-related documents only by their study ID numbers. The roster containing the unique identifying number and direct participant identifiers will be kept in a local password-protected database on a secure network drive at the clinical sites.

Almost all data will be entered in REDcap or Qualtrics. Only in rare cases will hard copy data collection forms be used, and this data will be entered like the data collected electronically within 1 week of collection and the hard copy will be subsequently destroyed. Data will be entered onto a secure Web-based data management system. Only the study coordinator and relevant research study staff will have access to this study database. Secure access will be assured by use of individual login codes and password protection. Entered data will be stored securely and accessed in accordance with current HIPAA standards, the HCFA's Internet Security Policy, and other state and local requirements.

All data interactions for the study by all users including participants, RDs, clinical staff, research staff, and investigators, are web-based communications between the given user's web browser and the web server running the study website and/or data management software. All of these web-based communications are configured to use the standard HTTPS protocol with 128-bit encryption. This includes online forms submitted by participants as they are transferred to the servers at UNC.

For the purposes of tracking recruitment, scheduling, and reminders, basic participant information, including first and last name, Study ID, and dates and other pertinent information regarding scheduled appointments (reminder calls, etc.) will be kept in a password-protected Microsoft Access database stored securely at each clinical site.

As is the case with all behavior intervention utilizing current technology, particularly mobile phones, we will explain to participants that transmission of such information is not secure.

All aspects of data collection and data storage will be carefully monitored to ensure rapid detection of errors, inconsistencies or other problems. The data collectors will follow a strict written protocol that describes study measures for protecting data privacy, explain to each participant that s/he has the right to refuse to participate or to refuse to answer any individual question that s/he finds objectionable, and emphasize the importance of telling the truth. All institutions associated with this study are experienced in training data collection fieldwork personnel how to handle, store, and process sensitive and confidential data. Certain routine administrative, personnel, physical security, information management, and computer system or network security practices are always in place. These practices include non-disclosure pledges, and account/keyword security on computer networks.

In addition, we take multiple project-specific steps to protect subjects from the risk of a breach in confidentiality. All data will be collected using study ID numbers. Thus, no questionnaire will contain identifying information, and the roster containing the unique identifying number and direct participant identifiers will be kept in a local password-protected database on a secure network drive at the clinical sites. Finally, only aggregate data that cannot be used to identify individuals will be included in any reports released to other agencies or for publication.

16. Study Timeline

The study is planned to complete in May 2023. The timeline is as follows [see detailed table in spreadsheet]:

IRB approval: March 2021

Staff training: April/May 2021

Participant recruitment: October 2021

Intervention: December 2021 – May 2023

Analysis, Abstract and Publication preparation: January – December 2024

Bibliography

f

1. Effect of intensive diabetes treatment on the development and progression of long-term complications in adolescents with insulin-dependent diabetes mellitus: Diabetes Control and Complications Trial. Diabetes Control and Complications Trial Research Group. *JPediatr* 1994; **125**(2): 177-88.

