Test Article(s)	
 • Individualized planned eating plan with the following five behavioral targets (“MyPlan goals”): 
 ○ 3-4 meals and 0-2 snacks consumed; ○ Meals/snacks consumed >2 hours and <4 hours apart ○ Carbohydrate (CHO) distributed across waking hours (meals >15% daily CHO, with ~10-15% of daily CHO at snacks and ~20-30% at meals) ○ No snack consumed after dinner; ○ Snack/meal consumed 1-2 hours of waking. • If relevant, snacks will be recommended based on the participants’ usual food intake, age, sex, activity and growth • Participant and family-specific eating schedules and routines will be incorporated into each individualized planned eating plan. • Behavioral counseling strategies will identify barriers to adherence and acceptability and address them through targeted education, problem solving and goal setting skills training.
Study Design	
This is a pilot single arm clinical trial to assess whether planned eating is an acceptable and effective dietary strategy to be included in future fully powered trials aimed at optimizing diabetes outcomes in T1D youth.
 
This pilot study will be conducted at two clinical sites (University of Cincinnati, and University of North Carolina at Chapel Hill), coordinated from the University of North Carolina at Chapel Hill. Approximately 33 teen/guardian dyads will be enrolled at University of Cincinnati and 17 at UNC for a total of 50 enrolled participant/guardian dyads (with 40 or more expected completers).

A total study participation time of 6-months allows for evaluation of the acceptability of and adherence to the eating strategy and its influence on glycemic levels (comparing percent time within the glycemic range 70-180 mg/dL during 2-week wear time at baseline and 6 months).

Following the baseline data collection and a 2-week run-in period, all participant dyads will be counseled to follow an individualized planned eating plan developed based on caloric needs, usual physical activity level, food preferences, previous intake and participant/family eating schedules.

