Study Phases	1. Screening and Pre-Intervention Data Collection: Screening for eligibility, recruiting and obtaining consent; Collection of basic demographic, health, diabetes knowledge, eating and physical activity pattern information via

	
questionnaires at baseline visit. HbA1c, height, and weight measurements at baseline visit.
 
 2. Run-in (2 weeks): Set-up mobile device and text reminders for mobile data collection; Collection of daily logs and two 24-hour recalls to inform eating plan designed by RD; 2-week CGM wear. 3. Intervention (22 weeks): Study intervention 4. Post-Trial Data Collection: Completion of eating plan acceptability Assessment, questionnaires, 2-week CGM wear, HbA1c, height, weight measurements.
Safety Evaluations	Participants will be asked about hypoglycemic events at each study visit and support session with the RD (by phone or in-person). Participants will be instructed to contact the study endocrinologist and/or RD to report any cases of severe hypoglycemia. The RDs will communicate with the study endocrinologist to ensure that any needed insulin adjustments are made throughout the study period. Participants will be encouraged to monitor their weight at home throughout the study period. Weight and height will also be collected at baseline, 3 months, and 6 months to monitor any changes and ensure healthy maintenance of weight and growth.
Statistical and Analytic Plan	
Adherence outcome:
 
 • Planned eating adherence (primary measures): Weekday and weekend adherence to five eating behavior targets/goals that define the MyPlan strategy will be calculated continuously and categorically. Additional measures will include adherence consistency, defined as the extent to which youth performance on the adherence metrics differs between the dietary recall days, as well as proportion of completed telehealth visits/phone calls, and diet-self-monitoring days (exploratory measures). 
Acceptability outcome:
 
 • Categorical and continuous 5-item measure of acceptability (primary measures) • Additional measures include qualitative information, which will be analyzed for themes (exploratory measures). 
Glycemic outcomes:
 
 • Percent time in the glycemic range 70-180mg/dL comparing CGM wear time at baseline and 6 months (primary measure) • HbA1c (secondary measure)

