0.52%.²⁴ We will collect HbA1c as a secondary outcome measure. We will conduct exploratory analyses to determine if change in glycemic control differs according to degree of adherence to planned eating and other clinical and demographic factors. As part of the planned post-hoc qualitative evaluation of the MyPlan project with a sub-sample of participants and their parents, we will assess self-reported/subjective effectiveness and more deeply explore potential reasons underlying why MyPlan may have improved or failed to improve participants' glycemic management to identify intervention levers for future studies.

4. Site Descriptions

The two clinical sites include 1) University of Cincinnati in Ohio) and 2) University of North Carolina Medical System. All clinical sites are well-established academic medical centers with vast experience in diabetes translational research. UNC-CH will oversee coordination of the pilot trial. The study investigators across UNC-CH and University of Cincinnati have over a decade of collaborative experiences in research among youth with T1D, and comprise the core team for the future trial for which these pilot data are being collected.

5. Selection & Recruitment of Subjects

Exclusion criteria: The following individuals will be excluded from study participation. Individuals with other metabolic disorders, unstable thyroid disease, diagnosed eating disorder, prohibitive strict dietary restrictions, or those with other serious condition that renders participation inappropriate. Females who are currently pregnant will be excluded.

Inclusion criteria: Male and female individuals ages 12-17 years old with a diagnosis of type 1 diabetes of greater than one year, and a HbA1c measurement between 7.5-11% in the preceding 9 months. A parent (or legal guardian) will also be included for each participant.

Recruitment will use a combination of in-person and remote strategies:

Introductory Recruitment Step “Initial Contact”:

Medical records will be used to identify adolescents who potentially meet the eligibility criteria for this study. A mix of active and passive recruitment strategies will be used to establish initial contact with potential participants:

- We will work with NC TraCS to establish recruitment through MyChart.

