Alignment of participant behavior to the prescribed eating behavior pattern will be objectively assessed via two unannounced 24-hour dietary recalls (1 weekday, 1 weekend per week) collected during the 0-2 week and 22-24 week CGM wear time of the MyPlan study. Adherence metrics (weekday and weekend) will include proportion of participants who followed each eating behavior target, proportion of participants who met 0-5 eating behavior targets, and average number of targets met

In exploratory analyses, participant logs and 24-hr recalls will also enable identification of which snacks/meals are most often missed, which snacks/meals deviate the most from time or carbohydrate distribution targets as specified in the planned eating plan, as well as which aspects of regular eating pose the biggest challenges to adherence. These metrics will help with targeting counseling and focusing goal-setting, as well as areas to focus the design of future trials.

Eating behavior pattern acceptability

Although acceptability of the individualized planned eating plan will be ascertained every week after the plan is introduced, acceptability will be reviewed formally at 3 months, and again at the conclusion of the intervention period. Participants and their parent/guardians will fill out an acceptability assessment that we have used in previous studies.^{101 17} We will calculate separate composite acceptability scores (5 highly acceptable, 20 highly unacceptable, >10 unacceptable) from ordinal responses to statements from an 5-item instrument designed to capture ease of eating pattern

adoption, satisfaction, food enjoyment, sustainability, and ease of blood sugar management. As part of the post-hoc qualitative evaluation of the intervention, we will conduct short semi-structured qualitative exit interviews with teenager and parent participants and project staff to ascertain barriers and facilitators to following the eating strategy, likes and dislikes, recommendations for modifications, likelihood of recommending the strategy to others, and the eating behavior target participants found most difficult to follow, alongside other feedback related to intervention design, materials, and implementation.

8b. Secondary Outcomes

HbA1c

At baseline and 26 weeks, HbA1c will be measured using point-of-care testing.

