To assist participants and families in planning meals and snacks that align with participants’ individualized planned eating plans, participants will be given a subscription to MyFitnessPal Premium, which will also conveniently serve as the platform through which mobile phone logs are collected. Any changes to the personalized eating plan made throughout the study will be captured in Qualtrics.

Because it is possible that planful eating may also affect types of foods consumed, we will also administer a food frequency questionnaire at baseline and end of the study to capture dietary quality throughout the study.

MyFitnessPal logs

Eating pattern and physical activity will be monitored via participant mobile phone logs collected through MyFitnessPal.

In addition to the 24-hour dietary recalls, the logs collected during the first two weeks will be used to understand participants’ preferred foods and timing of snacks and meals. This information will inform the design of the individualized planned eating plan. This information will also be used to inform the design of a sample menu of meals and snacks that will be introduced to and adjusted with the participant on the first week of the active intervention (week 3). Participants will therefore be instructed to follow their usual eating and physical activity habits during this run-in week, and RDs will emphasize that honesty in logging usual habits will optimize the RD’s ability to design a planned eating plan that fits into the participant’s lifestyle and is sustainable. Once the planned eating plan has been designed and delivered to the participant in the first week of the active intervention (week 3), subsequent logs collected throughout the intervention period will facilitate discussions about challenges with adherence, focus problem solving and goal setting, and inform needed adjustments to the planned eating plan. As discussed in a subsequent section, adherence to logging will be used to allocate points/incentive money to participants throughout the study.

[figure not shown]
Other Health Information

At the Pre-Trial Data Collection Visit, we will conduct a medical chart review to collect basic demographics, including birth date, sex, ethnicity, and race. Medical chart review will also enable ascertainment of date of diabetes diagnosis, diabetes care (i.e. insulin regimen), and other relevant health history.

9. Trial Procedures and Components

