Power analyses are based on matched-pairs t-tests and a conservative estimate of 40 participants (alpha level of 0.05). Drawing from our previous study with a similar population to estimate the within-subject correlation, we have 80% power to detect an improvement in TIR of 10%.⁹⁴ In this previous study, the average TIR was 34.7% (SD=13.6), so this would correspond to an increase to an average of 42.5% TIR. The detectable effects are large, which is appropriate in this study that aims to assess preliminary effectiveness and acceptability to inform the design of a future fully-powered RCT of longer duration.

Outcome evaluation

Aim 1. Assess acceptability and adherence to a 6-month individualized planned eating intervention (“MyPlan”) among 40 youth with T1D.

1) Adherence:

We will calculate and report continuous and categorical overall adherence to the eating behavior pattern and adherence specific to each of the five eating behavior targets that make up the pattern (i.e. mean number of eating behavior targets met, proportion of participants who met each type of target, proportion of individuals who met 0, 1, 2, 3, 4, or 5 targets). Further exploratory modeling will be conducted to identify the contributions that adherence to each of the five individual behavioral targets make to overall adherence scores, as well as the relative magnitude of associations between adherence to each of the five individual behavioral targets and glycemic measures.

Acceptability:

- We will calculate continuous and categorical participant and guardian acceptability of the eating behavior pattern. Additional analyses include combined composite scores, exploratory modeling of demographic, clinical, and psychosocial predictors of acceptability will be conducted to inform both recruitment and targeted counseling strategies in future trials. We will assess acceptability related themes that emerge from answers to questionnaire free response items and questions posed as part of the qualitative post-hoc analysis of the intervention.

Aim 2. Compare glycemic control among adolescents with T1D at baseline and at the end of the 6month MyPlan intervention.

2) Effect on glycemic control:

We will compare continuous difference in TIR under the eating behavior pattern (22-24 weeks) vs. usual diet (0-2 weeks). We hypothesize that a) $TIR_{MyPlan \text{ eating behavior pattern}} > TIR_{\text{usual diet}}$

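### Does the approximate carbohydrate target need a graded adherence score instead of met / not met?

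*Combined protocol and SAP*

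**What the plan says.** The only numerical statement of the carbohydrate target is in the Protocol Synopsis, Test Article(s): "Carbohydrate (CHO) distributed across waking hours (meals >15% daily CHO, with ~10-15% of daily CHO at snacks and ~20-30% at meals". Section 3 repeats the target without numbers.

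Section 11, Aim 1, promises "continuous and categorical overall adherence to the eating behavior pattern", and illustrates this with the "mean number of eating behavior targets met, proportion of participants who met each type of target" and the distribution of 0 to 5 targets met. Section 8a, Eating behavior pattern adherence, has the same list: the proportion following each target, then the "proportion of participants who met 0-5 eating behavior targets, and average number of targets met". Each needs a yes or no for every target. The data are one weekday and one weekend dietary recall in each CGM period (weeks 0-2 and 22-24).

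Section 8a also plans an exploratory look at "which snacks/meals deviate the most from time or carbohydrate distribution targets as specified in the planned eating plan", which is not a yes/no measure. The Synopsis says that the run-in recalls feed the eating plan: "Collection of daily logs and two 24-hour recalls to inform eating plan designed by RD". Section 3, Aim 2, classes the link between adherence and glycemia as exploratory: "We will conduct exploratory analyses to determine if change in glycemic control differs according to degree of adherence to planned eating".

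**The concern.** A count of targets met needs a sharp cut, and this target is not written as one. An analyst could score the floor alone, or the floor plus the shares with a few points allowed for the approximation sign. The same eating would then give different values for the proportion meeting the target and for the mean count. Both are Aim 1 primary measures meant to inform the next trial. Even the continuous measure named in Section 11 is a count of yes/no results, so it discards information in a pilot of about 40 completers.

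The proposed remedy was a graded score: for each eating occasion, the percentage points by which its share lies outside the printed range, averaged over the day. It was said to need no cut and to detect change better.

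**Working it through.** The documents give no figure for adherence to this target and no day-to-day variation, so there is no figure of theirs to reproduce. Everything below rests on assumptions.

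**Inputs.** From the Synopsis: meal floor above 15%, meals about 20-30%, snacks about 10-15%, with 3-4 meals and 0-2 snacks a day. Assumed: planned shares of 25 per meal and 12.5 per snack, rescaled to 100. Grams per occasion vary independently (lognormal) with a CV of 10, 20, 30 or 40%. Share = grams / day total. There were 400,000 simulated days per cell.

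**Step 1. How far the readings differ for youth fully on plan.** Percentage of days met, mean of four patterns (meals+snacks: 3+1, 3+2, 4+0, 4+1):

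| CV | Floor alone | Shares ±5 | Shares ±4 | Printed edges exactly |
|---|---|---|---|---|
| 10% | 100.0 | 99.6 | 98.9 | 59.5 |
| 20% | 97.6 | 87.3 | 79.6 | 19.1 |
| 30% | 84.8 | 60.4 | 49.1 | 6.8 |
| 40% | 67.6 | 38.0 | 28.4 | 3.1 |

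At a CV of 20%, floor minus ±4 is 97.6 - 79.6 = 18.0 points. That is 0.18 × 40 = 7.2 participants, or 0.18 on the 0-5 mean count. At 10% it is 1.1 points.

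**Step 2. Where the gap comes from.** By pattern at 20%, the gap is 42.8 (3+1), 9.5 (3+2), 10.8 (4+0) and 9.2 (4+1). The mean of all four is 72.3 / 4 = 18.1, which matches Step 1 apart from rounding. Without 3+1 it is 29.5 / 3 = 9.8 points, or 0.098 × 40 = 3.9 participants. The reason is arithmetic: on 3+1 each meal is planned at 25 / 87.5 = 28.6%, only 1.4 points below the printed upper edge.

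**Step 3. Whether a graded score avoids the choice.** Distance outside the printed range sets the tolerance for the approximate edges to zero. By those edges, on-plan youth at a CV of 20% fall outside on 100 - 19.1 = 80.9% of days. The score also ignores the floor: a meal at 16% clears 15% yet counts 20 - 16 = 4 points off. Mean scores for equally on-plan youth at 20% are 0.43 (3+2), 1.19 (3+1) and 4.16 (3+0), although the first target allows all three. Leaving out an optional snack would register as poorer adherence.

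**Step 4. Whether it detects change better.** Eight assumed baseline splits × four CVs give 32 scenarios. Each youth moves a random fraction of the way to plan, and the score is the mean of two days. Standardized change relative to the best rule:

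| Rule | Median | Minimum |
|---|---|---|
| Graded, zero tolerance | 1.00 | 0.96 |
| Graded, 4-point tolerance | 0.91 | 0.36 |
| Floor alone | 0.84 | 0.14 |
| Shares ±5 | 0.76 | 0.32 |
| Shares ±4 | 0.72 | 0.44 |

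Squaring the medians for the yes/no rules gives 40 × 0.84² = 28, 40 × 0.76² = 23 and 40 × 0.72² = 21 effective participants. The graded score's near-uniform lead depends on the zero tolerance. In the four splits with a meal at or below 15%, the floor's median is about 0.97, or 40 × 0.97² = 38. Every scenario keeps the number of meals fixed, so skipped meals, which motivate the trial in Section 2, are not represented.

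**Step 5. Three meals and no snack.** Read literally, 3 × 30 = 90%, short of 100. The shortfall per meal is 100/3 - 30 = 3.3 points.

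**The case for a change.** The strongest case for a change is that adherence is an Aim 1 primary outcome and its level should reflect eating, not a cut chosen after the data are seen. For incentive goals the protocol does write down what counts as met (Table 2, note 1); for the recall-based outcome it does not. The recalls already hold what is needed, so a rule costs a paragraph and a short script. In the simulations a graded score was best in 25 of 32 scenarios. Scoring against the individual eating plan would not help with change from baseline, because the baseline recalls help shape that plan.

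The missing rule is real, and above a CV of about 10% the reading affects the reported proportion. The caution about the individual plan is also fair, although the five printed targets are common to everyone and can be applied at both time points as they stand.

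The claim for the graded score does not stand. It embodies one reading of the target, depends on the number of snacks, and loses its near-uniform lead once the same 4-point tolerance is allowed. Nor can it supply the 0-5 count, which would still need a cut. The comparison concerns a pre-post change in this one target, which the plan does not set out to test; regression models (b) and (c) use overall adherence, which was not simulated.

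**Conclusion.** No change to the plan is needed. The gap is a missing scoring detail for one of five targets. The outcome is descriptive, with no hypothesis test and no progression cutoff attached. An analyst would choose a reading, apply it at both time points and report it; showing the other reading beside it is ordinary practice. Replacing the continuous measure would exchange one debatable choice for another.

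At an assumed CV of 20% the choice moves the proportion by about 9 to 11 points for the 3+2, 4+0 and 4+1 patterns and by about 43 for 3+1. At 10% the average difference is about 1 point; at 30% and 40% it is about 36 and 39. These figures rest on assumed CVs, independent occasions, equal weight for four patterns and a 4-point tolerance, none of which the documents give.

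The first and third targets do not fit together literally for three meals and no snack. The shares are marked approximate, so this is a point of wording for the study team to reconcile and not a statistical defect. The pre-post comparison of time in range and its power are unaffected.
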